6.5.6 Premature patient withdrawal from study treatment

Patients *may* voluntarily withdraw from study treatment or study treatment may be discontinued at the discretion of the investigator at any time. Patients must be withdrawn prematurely from the study treatment if any of the following occur:

- premature discontinuation of study drug (see [section 6.5.5](#))
- pregnancy
- graft loss / re-transplantation
- third severe rejection episode (ISHLT 1990 grade \geq 3A resp. ISHLT 2004 grade \geq 2R) with or without hemodynamic compromise or rejection episode requiring change in baseline immunosuppressive therapy according to this protocol or any rejection ISHLT 1990 grade \geq 3A resp. ISHLT 2004 grade \geq 2R within months 6 – 9 **(as assessed by per protocol biopsies)**
- occurrence or detection of severe medical disorder jeopardizing the life of the patient in the immediate future

If such premature withdrawal from study treatment occurs, or if the patient fails to return for visits, the investigator must determine the primary reason for a patient's premature withdrawal from the study and record this information on the Study / Treatment Completion CRF.

Patients may be withdrawn from the study treatment prematurely at the investigator's discretion for one of the following reasons:

1. adverse event(s)
2. abnormal laboratory value(s)
3. abnormal test procedure result(s)
4. unsatisfactory therapeutic effect (e.g. severe rejection)
5. protocol violation
6. administrative problems
7. patient's condition no longer requires study treatment

In cases of recurrent infections serum antibody concentration should be measured; if hypogammaglobulinemia presents as persistent and clinically significant, patients should be examined accurately and appropriate actions should be taken; MPA dose reduction or change of MPA-based immunosuppression should be taken into consideration.

Patients with recurrent pulmonary disorders e.g. cough/dyspnea should as soon as possible be examined accurately for signs of bronchiectasis; MPA dose reduction or change of MPA-based immunosuppression should be taken into consideration.

For patients who are lost to follow-up, the investigator should show “due diligence” by documenting in the source documents steps taken to contact the patient, e.g. dates of telephone calls, registered letters, etc.

Patients who discontinue participation in the trial for any reason will not be replaced.

All patients who prematurely discontinue study treatment should still attend the final visit at Month 18 post transplantation to obtain follow up information on rejection episodes, allograft and patient survival, hospitalizations, malignancies and immunosuppressive medication.

The CRFs Study Completion Page should be completed at month 18 or earlier if the patient can no longer be followed, e.g. due to death, withdrawal of consent, or loss to follow-up.

6.5.7 Emergency unblinding of treatment assignment

Not applicable, since this is an open-label trial.

7 Visit schedule and assessments

Table 7-1 lists all of the assessments and indicates with an “X” the visits when they are performed. All these obtained data must be supported in the patient’s source documentation.

Table 7-1 Assessment schedule

Phase	Prephase	Study Drug Treatment					
		SCR	BL	Switch	Maintenance		
Period	1	2	3	4	5	6	7 ¹ /7.1 ²
Visit	1	2	3	4	5	6	7 ¹ /7.1 ²
Month post Tx	3	6	8	9	10	12	18
Informed consent	X						
Inclusion/ exclusion	X		X				
Randomization			X				
Demography	X						
General medical history	X						
Renal history (information on dialysis etc.)	X						
Transplantation information	X						
Physical examination	X	X		X			X
Vital signs	X	X	X	X	X	X	X
Endomyocardial biopsy		X		X		X	X
ECG	X	X		X		X	X
Study medication check		X	X	X	X	X	X
Laboratory test:							
- Hemat. / Biochemistry	X	X	X	X	X	X	X
- Viral Serology	X	X ³	X ³	X ³	X ³	X ³	X ³
- Pregnancy test ⁴ (β-HCG)	X	X	X	X	X		X
- Blood sampling for frozen storage (2-5 mL EDTA blood)	X	X		X			X
- Urinalysis (proteinuria)	X	X		X			X
Drug concentration (C0-h)							
Tacrolimus/ Cyclosporin A ⁵	X	X	X	X	X	X	X
Everolimus	X	X	X	X	X	X	X
Comments				as necessary			
Echocardiogram				as necessary			
Hospitalization ⁶				as necessary			
AEs				as necessary			
SAEs				as necessary			
Infections				as necessary			
Concomitant therapy				as necessary			
Positive inotropic effect or vasoactive treatment				as necessary			
Immunosuppressive therapy				as necessary			
Rejection episodes				as necessary			
Hemodynamic compromise				as necessary			
MACE				as necessary			
End of study ^{1/2}							X

SCR: Screening visit: Month 3 post Tx

BL: Baseline visit: day of randomization, Month 6 post Tx

- 1) At end of study (Month 18 post Tx) or at timepoint of discontinuation for patients with premature discontinuation of per protocol treatment
- 2) At Month 18 post Tx: Only for patients who prematurely discontinued the per protocol treatment
- 3) Only CMV-status (including pp65 Ag)
- 4) Only in women of childbearing potential
- 5) To be assessed only if Cyclosporin A or Tacrolimus is administered at that visit. C0-h levels have to be determined at all indicated timepoints.
- 6) Hospitalization: see [section 7.8](#), Resource utilization

Patients should be seen for all visits on the designated day or as close to it as possible. However, timely intervals of \pm 1 week will be regarded acceptable.

Screening Visit - Visit 1 (Month 3 post Tx)

This visit may be performed within a time window of \pm 2 weeks.

1. Patient signs informed consent.
2. Patient's eligibility for the study according to in- and exclusion criteria will be checked.
3. Demographic data will be recorded (sex, age, ethnic origin).
4. Relevant medical history as well as renal history (**especially information on dialysis**) will be obtained and recorded.
5. Transplantation information will be recorded (donor and recipient information, including viral serology; initiated immunosuppressive regimen, including induction therapy).
6. A complete physical examination will be performed.
7. Vital signs will be measured.
8. A 12-lead ECG will be written.
9. Venous blood will be drawn for measurement of hematology and biochemistry.
10. Viral serology of CMV (including pp65 Ag), Hepatitis B (HbsAg), Hepatitis C, and HIV will be recorded. Results from \leq 6 months prior Screening visit will be acceptable.
11. Venous blood will be drawn for measurement of the C0-h levels of Cyclosporin A or Tacrolimus and Everolimus.
12. Venous blood will be drawn for frozen storage until end of trial (2 EDTA-tubes, **2-5 mL**); only as a backup to repeat laboratory measurements if necessary).
13. In woman of childbearing potential a pregnancy test will be performed (β -HCG).
14. Urinalysis for proteinuria will be performed (spot urine sample for protein/creatinine ratio may be used).
15. Prior and concomitant medications / significant non-drug therapies will be recorded.
16. Immunosuppressive medication taken at M3 post Tx and any dose adjustments that were performed within the five days preceding the Screening visit will be recorded.

17. Information on rejection episodes and MACE that occurred since transplantation will be recorded.

Baseline Visit - Visit 2 (Month 6 post Tx)

This visit may be performed within a time window of \pm 1 week.

1. Patient's eligibility for the study according to in- and exclusion criteria will be checked
2. The patient will be randomized to one of the two treatment arms.
3. A complete physical examination will be performed.
4. Vital signs will be measured.
5. An endomyocardial biopsy will be performed.
6. A 12-lead ECG will be written.
7. Venous blood will be drawn for measurement of hematology and biochemistry.
8. Venous blood will be drawn for measurement of viral serology (CMV status including pp65 Ag).
9. Venous blood will be drawn for measurement of the C0-h levels of Cyclosporin A or Tacrolimus and Everolimus.
10. Venous blood will be drawn for frozen storage until end of trial (2 EDTA-tubes, **2-5 mL**).
11. In woman of childbearing potential a pregnancy test will be performed (β -HCG).
12. Urinalysis for proteinuria will be performed (spot urine sample for protein/creatinine ratio may be used).
13. Changes in Concomitant medications / significant non-drug therapies will be recorded.
14. (Changes in) immunosuppressive medication will be recorded.
15. Information on rejection episodes, hemodynamic compromise, MACE, hospitalization, infections, and other (S)AEs that occurred since the last visit will be recorded.

Switch of immunosuppressive regimen - Visit 3 (Month 8 post Tx)

This visit may be performed within a time window of \pm 1 week.

1. Vital signs will be measured.
2. Venous blood will be drawn for measurement of hematology and biochemistry.
3. In woman of childbearing potential a pregnancy test will be performed (β -HCG).
4. Venous blood will be drawn for measurement of viral serology (CMV status including pp65 Ag)
5. Venous blood will be drawn for measurement of
 - Everolimus C0-h level in all patients
 - Cyclosporin A C0-h level, only in patients of the CNI group

- Tacrolimus C0-h level, only in patients of the CNI group
- 6. Changes in concomitant medications / significant non-drug therapies will be recorded.
- 7. Changes in immunosuppressive medication (including study drug dosage) will be recorded.
- 8. Information on rejection episodes, hemodynamic compromise, MACE, hospitalization, infections, and other (S)AEs that occurred since the last visit will be recorded.

Maintenance Period - Visits 4, 5 and 6 (Month 9, 10, 12 post Tx)

These visits may be performed within a time window of \pm 1 week.

- 1. Vital signs will be measured.
- 2. An endomyocardial biopsy will be performed (only visits 4 and 6).
- 3. A 12-lead ECG will be written (not at month 10, Visit 5).
- 4. Venous blood will be drawn for measurement of hematology and biochemistry.
- 5. Venous blood will be drawn for the measurement of viral serology (only CMV-status including pp65 Ag).
- 6. Venous blood will be drawn for measurement of
 - Everolimus C0-h level in all patients
 - Cyclosporin A C0-h level, only in patients of the CNI group
 - Tacrolimus C0-h level, only in patients of the CNI group
- 7. In woman of childbearing potential a pregnancy test will be performed (β -HCG).
- 8. Changes in concomitant medications / significant non-drug therapies will be recorded.
- 9. Changes in immunosuppressive medication (including study drug dosage) will be recorded.
- 10. Information on rejection episodes, hemodynamic compromise, MACE, hospitalization, infections, and other (S)AEs that occurred since the last visit will be recorded.

Only at Visit 4, Month 9

- 11. A complete physical examination will be performed.
- 12. Venous blood will be drawn for frozen storage until end of trial (2 EDTA-tubes, **2-5 mL**).
- 13. Urinalysis for proteinuria will be performed (spot urine sample for protein/creatinine ratio may be used).

End of Study - Visit 7 (Month 18 and early discontinuation)

In case of early discontinuation, Month 18 assessments need to be performed

- as soon as possible after study drug discontinuation
- additionally at the originally planned timepoint, i.e. 18 months after transplantation

1. A complete physical examination will be performed.
2. Vital signs will be measured.
3. An endomyocardial biopsy will be performed.
4. A 12-lead ECG will be written.
5. Venous blood will be drawn for measurement of hematology and biochemistry.
6. In woman of childbearing potential a pregnancy test will be performed (β -HCG).
7. Venous blood will be drawn for measurement of viral serology (CMV-status including pp65 Ag).
8. Venous blood will be drawn for measurement of
 - Everolimus C0-h level in all patients
 - Cyclosporin A C0-h level, only in patients of the CNI group
 - Tacrolimus C0-h level, only in patients of the CNI group
9. Venous blood will be drawn for frozen storage until end of trial (2 EDTA-tubes).
10. Urinalysis for proteinuria will be performed (spot urine sample for protein/creatinine ratio may be used).
11. Changes in concomitant medications / significant non-drug therapies will be recorded (in case of early discontinuation until 30 days after last dose of study drug).
12. Changes in immunosuppressive medication (including study drug dosage) will be recorded (in case of early discontinuation until 30 days after last dose of study drug).
13. Information on rejection episodes, hemodynamic compromise, MACE, hospitalization, infections, and other (S)AEs that occurred since the last visit will be recorded
14. End of Study / End of Treatment information will be obtained.

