7.10 Pharmacokinetics

The actual sample collection times, and the date and time of the previous drug dose (Everolimus, Tacrolimus or Cyclosporin A) will be recorded on CRF using a 24 hour clock.

Cyclosporin/Tacrolimus A whole blood levels will be measured starting at Screening Visit. For patients of the CNI group Cyclosporin A/Tacrolimus blood level will be measured at every study visit, for patients of the CNI-free group Cyclosporin A/Tacrolimus blood level will be measured until Cyclosporin A or Tacrolimus is removed from the immunosuppressive regimen (Month 6 or 8 post Tx).

Everolimus blood levels will be measured in all patients starting at Screening Visit and at every study visit thereafter (if applicable).

- **Cyclosporin A (CsA) whole blood tests**

Analysis of the Cyclosporin A whole blood levels will be performed locally at the center. Whole blood level for CsA will be assessed within 5 minutes before the Cyclosporin A administration (C0-h level).

- **Tacrolimus (Tac) whole blood tests**

Analysis of the Tacrolimus whole blood levels will be performed locally at the center. Whole blood level for Tac will be assessed 5 minutes before the Tacrolimus administration (C0-h level).

- **Everolimus whole blood tests**

For the analysis of the Everolimus whole blood levels 2 ml of blood should be

drawn in EDTA tubes. The C-0h level will be obtained with blood sampling within 5 minutes prior to medication intake.

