10.6.7 Pharmacokinetics

Analysis of the Cyclosporin A, Tacrolimus and Everolimus blood levels will be done by treatment group and separately for the treatment phases (up to and after Month 6), the NRP group will be analyzed.

Everolimus

Mean blood level values of Everolimus will be presented in tabular form for each timepoint (visit window) and as mean value over time. Trough values will be tried to be kept in a therapeutic window of 5 – 10 ng/mL during the whole study. The number of patients with deviations from the therapeutic window will be counted (separately for values “below” and “above” therapeutic range) and tabulated per visit and in total.

Patients with any trough level value outside the therapeutic window will be described in detail by narratives reporting also Everolimus dose level and dose adjustments, if applicable.

Cyclosporin A

Mean blood level values of Cyclosporin A will be presented in tabular form for each timepoint and as mean value over time. Blood levels will be tried to be kept in therapeutic windows. The number of patients with deviations from the therapeutic window (see [section 6.5.2](#)) will be counted and tabulated per visit and in total.

In the CNI-free group mean blood level values of cyclosporin A will be presented in tabular form for each assessment up to Month 8.

Tacrolimus

Mean blood level values of Cyclosporin A will be presented in tabular form for each timepoint and as mean value over time. Blood levels will be tried to be kept in

therapeutic windows. The number of patients with deviations from the therapeutic window (see [section 6.5.2](#)) will be counted and tabulated per visit and in total.

In the CNI-free group mean blood level values of Tacrolimus will be presented in tabular form for each assessment up to Month 8.

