## **2.8 Pharmacokinetic endpoints**

Analysis of the Cyclosporin A, Tacrolimus and Everolimus blood levels were done by treatment group and separately for the treatment periods (after Month 6).

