### **Cyclosporin A:**

Mean blood level values of Cyclosporin A were presented in tabular form for each timepoint and as mean value over time. Blood levels were tried to be kept in therapeutic windows. The number of patients with deviations from the therapeutic window (see section 5.1.4 Target therapeutic ranges) were counted and tabulated per visit and in total.

In the CNI-free group mean blood level values of cyclosporin A were presented in tabular form for each assessment up to Month 8.

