### **Tacrolimus:**

Mean blood level values of Tacrolimus were presented in tabular form for each timepoint and as mean value over time. Blood levels were tried to be kept in therapeutic windows. The number of patients with deviations from the therapeutic window (see section 5.1.4 Target therapeutic ranges) were counted and tabulated per visit and in total.

In the CNI-free group mean blood level values of Tacrolimus were presented in tabular form for each assessment up to Month 8.

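### The Visit 3 (Month 8) list limits CNI troughs to the CNI group, contradicting Table 7-1 footnote 5 and section 7.10, so the planned Month 8 CNI-free level may not be drawn

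*Protocol*

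**What the plan says.** **Visit lists (protocol section 7).** At Visit 3 (Month 8), everolimus troughs are drawn in all patients. The CNI lines read "Cyclosporin A C0-h level, only in patients of the CNI group" and "Tacrolimus C0-h level, only in patients of the CNI group". The same two lines appear in the shared list for Visits 4 to 6 and in the Visit 7 list.

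**Assessment schedule (protocol Table 7-1).** The CNI trough is marked at every visit, Month 8 included. Footnote 5 sets the condition: "To be assessed only if Cyclosporin A or Tacrolimus is administered at that visit". It adds that levels are mandatory at all marked timepoints.

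**Pharmacokinetics (protocol 7.10).** CNI-free patients are to be measured "until Cyclosporin A or Tacrolimus is removed from the immunosuppressive regimen (Month 6 or 8 post Tx").

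**Taper (protocol 6.5.1, 6.5.2 and Table 6-1).** From the day after randomization, CNI-free patients go to cyclosporin ≤75 ng/mL or tacrolimus ≤5 ng/mL for 8 weeks, followed by removal. The whole process may take up to 3 months, ending at Month 9.

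**Planned output.** Protocol 10.6.7 states: "In the CNI-free group mean blood level values of cyclosporin A will be presented in tabular form for each assessment up to Month 8". It plans the same for tacrolimus. SAP 2.8 repeats both: "In the CNI-free group mean blood level values of cyclosporin A were presented in tabular form for each assessment up to Month 8" and "In the CNI-free group mean blood level values of Tacrolimus were presented in tabular form for each assessment up to Month 8".

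**The concern.** Three parts of one protocol give two different rules for the same blood sample. Footnote 5 and section 7.10 depend on drug exposure; the visit lists depend on the randomized arm. For a CNI-free patient still tapering at Visit 3, the two rules cannot both be followed.

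At stake is one descriptive row, the mean CNI level in the CNI-free arm at Month 8. The row has some value. SAP 5.1.4 lists the reduced switch targets, and SAP 2.8 counts patients outside their therapeutic window. The Baseline sample precedes the taper, so Visit 3 is the only scheduled visit before Month 9 that can show whether the reduced levels were reached. There is no scheduled reserve either: Table 7-1 and the visit lists place frozen EDTA storage at Visits 1, 2, 4 and 7, not Visit 3.

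**Working it through.** The plan states no figure to reproduce here. The check is whether a CNI-free patient can be on a CNI at Visit 3, and what then happens to the sample.

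**Inputs**
- Visit 2 at Month 6 and Visit 3 at Month 8, each with a window of ±1 week (protocol section 7).
- Taper of 8 weeks, then removal, starting the day after randomization (Table 6-1, 6.5.1).
- Latest stop at Month 9 (6.5.1, 6.5.2).
- 162 patients randomized 1:1 (SAP 1.1).
- Assumed month length: 365.25 / 12 = 30.4375 days.

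**Calendar**
1. Nominal gap from Visit 2 to Visit 3: 2 × 30.4375 = 60.9 days.
2. With both windows used in full, the gap runs from 60.9 − 14 = 46.9 days to 60.9 + 14 = 74.9 days.
3. The 8 weeks end at day 56, or day 57 if counted from the day after randomization.
4. The latest permitted stop is 3 × 30.4375 = 91.3 days.

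A patient exactly on schedule is therefore off the CNI 4 to 5 days before nominal Visit 3. A patient whose visits fall less than 8 weeks apart, or whose taper runs past 8 weeks, can still be on it.

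**How many.** The CNI-free arm is about 162 / 2 = 81. If all stop at 8 weeks and attend on the nominal day, 0 are on a CNI at Visit 3. If all taper past Visit 3, about 81 are. The documents do not narrow this range.

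**The rules side by side, for CNI-free patients**

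| Situation | Footnote 5 and 7.10 | Visit list |
|---|---|---|
| Visit 3, CNI already stopped | no level | no level |
| Visit 3, still on CNI | level required | no level |
| Visit 4, taper unfinished | level required | no level |
| Visit 7 as early-discontinuation visit, on CNI | level required | no level |
| Visits 5 and 6, on protocol | no level (no CNI taken) | no level |

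The Visit 7 case arises because protocol 6.5.5 requires the final-visit assessments when study drug is stopped early. That can happen during the taper. Therapy after the protocol regimen ends is also at the investigator's discretion (7.1), so it may include a CNI.

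**The case against.** The strongest reply is that the sample is required elsewhere. Table 7-1 is the master list, footnote 5 is explicit, and 7.10 names the CNI-free group. Sites also cannot dose to ≤75 or ≤5 ng/mL without measuring troughs. On the nominal 8-week taper there is no conflict at Visit 3 at all. This stands as a limit on the size of the problem. It does not remove the contradiction, and a trough taken for dosing need not be drawn or recorded as the Visit 3 value.

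Two stronger readings are tempting.

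- **That the whole CNI-free summary rests on this one sample.** SAP 2.8 opens by analysing levels "separately for the treatment periods (after Month 6"), which a reader might take to exclude everything before Visit 3. The documents do not force that. Protocol 10.6.7 covers the phases both up to and after Month 6, troughs are drawn in all patients at Screening and Baseline, and SAP 5.1.1 starts the randomized period at the Month 6 visit. Only the Month 8 row is at risk.
- **That the number affected can be estimated.** Suppose everyone stops at 8 weeks and both visits are spread evenly over their windows. The share still on a CNI is (14 − 4.875)² / (2 × 14²) = 83.27 / 392 = 21%, about 17 of 81. Counting the 8 weeks to day 57 gives (14 − 3.875)² / 392 = 102.52 / 392 = 26%, about 21. Nothing in the documents supports the even spread, and a one-day choice moves the answer. These figures are not estimates.

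**Conclusion.** The Visit 3 trough lines are wrong as written. This is a minor internal inconsistency rather than a design choice: nothing suggests that anyone meant to leave the sample out.

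The effect is confined to the Month 8 CNI-free row of a descriptive exposure table, plus possible gaps at Visit 4 and at early-discontinuation visits. Between 0 and about 81 patients could be concerned, assuming the 1:1 allocation gave near-equal arms. The Month 3 and Month 6 levels and the primary GFR analysis are not affected, and CNI doses and durations are summarised by arm regardless (SAP 2.4.1). A reader might infer that samples were missed; the documents show only that the instructions allowed it.

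**What to change.** 1. **Protocol section 7.** In the trough lines of Visits 3, 4 and 7, replace the restriction to the CNI group with: in all patients receiving Cyclosporin A or Tacrolimus at that visit. Visits 4 to 6 share one list, so the change carries to Visits 5 and 6, where it is harmless. It asks for no sampling beyond Table 7-1. The edit is a few words, but Appendix 1 requires a written amendment with sponsor and ethics committee approval, and health authority approval where required.

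2. **SAP 2.8.** In the Month 8 CNI-free row, show for each CNI the number of patients still taking it and the number with a level. A reader can then tell a patient who was off the CNI from one who was not sampled. Dosing dates are already recorded (protocol 7.4) and dosing records already assigned to visits (SAP 2.4.1), so the cost is two counts per drug in one table.

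The second change is likely to be the useful one for this trial. Enrollment at Month 3 ended on 31 December 2015. Visit 3 follows 5 months later, so on schedule the last would have been held around mid-2016, about a year before the SAP date of 2 June 2017. Rewording cannot recover a level that was not drawn, but the counts would show whether any are missing.
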